7.3. Caution

(1) Prior to using this device, physicians must receive specialized professional training and maintain a thorough understanding of the principles, clinical applications, complications, adverse reactions, and potential risks of aortic stent graft procedures.

(2) This procedure typically involves the combined use of one integrated ascending aortic stent graft, one integrated aortic arch segment stent graft, and three branched stent grafts. Implantation of an additional aortic extension stent graft may be determined based on the patient's vascular anatomy. To effectively prevent endoleak, appropriate specifications and models for the

integrated ascending aortic stent graft, integrated aortic arch segment stent graft, aortic extension stent graft, and branched stent grafts shall be selected preoperatively.

(3) During advancement and positioning of the integrated ascending aortic stent graft system, positioning shall be guided by the proximal and distal radiopaque markers on the main stent graft, as well as the radiopaque markers at the integrated branch regions, to align these markers with the predetermined optimal deployment position.

(4) During advancement and positioning of the branched stent graft systems for the innominate artery and left common carotid artery, the positional relationship between the proximal radiopaque markers and the proximal radiopaque rings of the integrated branches within the lumen of the main integrated ascending aortic stent graft shall be considered; meanwhile, the positioning of the distal radiopaque markers within the corresponding branch arteries shall be ensured.

(5) During advancement and positioning of the integrated aortic arch segment stent graft system, the positional relationship between its proximal radiopaque markers and the previously deployed proximal segments of the innominate and left common carotid branched stent grafts shall be considered; the fenestration radiopaque markers shall be aligned with the orifice of the left subclavian artery.

(6) During advancement and positioning of the branched stent graft system for the left subclavian artery, the positional relationship between its proximal radiopaque markers and the distal radiopaque rings of the integrated branches within the lumen of the main integrated aortic arch segment stent graft shall be considered; meanwhile, the positioning of the distal radiopaque markers within the left subclavian artery shall be ensured.

(7) During advancement and positioning of the aortic extension stent graft system, the positional relationship between its proximal radiopaque markers and the distal radiopaque markers of the previously deployed integrated aortic arch segment stent graft shall be considered.

(8) After accurate positioning of the integrated ascending aortic stent graft, integrated aortic arch segment stent graft, aortic extension stent graft, and branched stent grafts, the handle position shall remain stationary until full deployment of all stent grafts; otherwise, inaccurate stent

positioning may occur.

(9) When the proximal or distal end of the integrated ascending aortic stent graft is adjacent to critical arterial branches (e.g., coronary arteries, innominate artery, etc.), angiography or other imaging modalities may be used to assist positioning and prevent coverage or occlusion of vital branch vessels by the graft fabric.

(10) Once the integrated aortic arch segment stent graft system contacts the integrated ascending aortic stent graft during advancement, no further upward pushing of the delivery system shall be attempted for positional adjustment; otherwise, severe consequences such as migration of the integrated ascending aortic stent graft, vascular injury, or stent deformation may occur.

(11) During selective catheterization of the two integrated branches of the integrated ascending aortic stent graft, full confirmation that the guidewire passes entirely through the integrated branch lumens is mandatory.

(12) This device consists of the integrated ascending aortic stent graft system, integrated aortic arch segment stent graft system, aortic extension stent graft system, and branched stent graft system. Each component is preloaded in its dedicated delivery system and individually packaged.

(13) The Modular Integrated Triple-Branched Aortic Arch Stent Graft System is sterilized with ethylene oxide prior to factory release.

(14) This device is intended for single-use only. The manufacturer assumes no liability for cross-infection or adverse outcomes resulting from unauthorized reuse of any stent graft, delivery system, or component of this device. Do not use the product if the sealed packaging is damaged prior to opening.

8. Overall Design

8.1. Trial Design

8.1.1. Trial Objectives

This study is a pre-market clinical trial of the WeFlow-Tribranch embedded aortic Triple-branch arch Stent Graft system. It aims to evaluate the safety and efficacy of the system, developed and manufactured by Hangzhou Endonom Medtech Co., Ltd., in the endovascular interventional treatment of patients with aortic arch aneurysms, to provide clinical evidence for

the official domestic application of the device.

8.1.2. Trial Methodology and Rationale

This trial is designed as a prospective, multicenter, single-arm objective performance criterion clinical study.

Multicenter design: The trial will be conducted at multiple qualified domestic clinical centers. A multicenter approach facilitates patient enrollment, promotes benign competition among sites, and accelerates achievement of enrollment objective performance criterion. In addition, since subject data are collected from different regions and multiple centers by independent investigators, the final conclusions will be broadly representative.

Single-arm objective performance criterion design: Endovascular repair has become the preferred treatment for Stanford Type B thoracic aortic dissection; however, the management of lesions involving the ascending aorta or aortic arch remains challenging. Open surgery is the standard treatment for such diseases, yet it is associated with substantial surgical trauma, deep hypothermic circulatory arrest, antegrade/retrograde cerebral perfusion, and significantly elevated perioperative mortality and stroke rates. Patients enrolled in this trial generally present with aortic arch disease, advanced age, severe comorbidities, and are defined as high-risk individuals unsuitable for open surgery. Although existing thoracic aortic endovascular products can be modified and used off-label for aortic arch lesions, such structural adjustments lack adequate validation and carry potential safety and efficacy risks. Furthermore, no commercially available domestic device enables dual- or triple-branch reconstruction for supra-aortic arch vessels. Conservative medical treatment yields limited efficacy, and a more proactive intervention strategy is recommended for patients meeting intervention criteria. Setting a medical therapy control group would result in an extreme imbalance in risk–benefit profiles between the two arms. Therefore, a single-arm objective performance criterion design is adopted in this trial: a clinically meaningful objective performance criterion is predefined, and the safety and efficacy of the investigational device are evaluated without a parallel control group. The Guidelines for Clinical Trials of Transcatheter Implantable Artificial Aortic Valves issued by the NMPA recommend selecting clinically meaningful primary endpoints, with the 12-month cumulative all-cause mortality commonly proposed for sample-size estimation.

Considering the high clinical risk associated with ascending aortic and aortic arch diseases, and the anatomical proximity of the implant site to the aortic valve, the Guidelines for the Design of Medical Device Clinical Trials emphasize that primary endpoints should directly reflect clinical benefits and safety of the device. Accordingly, the primary endpoint of this trial is defined as the 12-month composite incidence of all-cause death or major stroke. In reference to the Guidelines for Clinical Trials of Aortic Stent Graft Systems, efficacy endpoints include the incidence of Type I or Type III endoleak, aortic stent graft migration rate, postoperative branch vessel patency rate, and conversion rate to open thoracic surgery or secondary interventional procedures. Safety endpoints comprise all-cause mortality, the incidence of serious adverse events, and the incidence of device-related adverse events. The objective performance criterion is established based on comprehensive, scientifically robust evidence from comparable marketed devices, while taking technological progress into account to ensure prospective rationality.

Medical records from five major hospitals in Honolulu, Hawaii, covering 1969 to 1977, reported 76 patients with atherosclerotic aortic aneurysms (including 10 involving the ascending aorta or aortic arch and 66 descending thoracic aortic aneurysms), with a mean age of 69 years and an estimated natural annual mortality of approximately 35%²⁴. A 2002 database from Yale University documented the natural history of 1,600 patients with thoracic aortic aneurysms: once the thoracic aortic diameter reached 6 cm, 31% of patients experienced aortic rupture or dissection; when the descending aortic diameter reached 7 cm, the risk of rupture or dissection increased to 43%¹¹, with a mortality rate of up to 90% for such events. Prognoses are even poorer for surgically high-risk patients with arch-located aneurysms. Regarding penetrating aortic ulcers (PAU), the Chinese Expert Consensus on the Diagnosis and Management of Acute Aortic Syndromes (2021 Edition) recommends proactive surgical or endovascular repair for symptomatic PAUs, or those with a diameter > 20 mm or depth > 10 mm, due to the high risk of progression to pseudoaneurysm or rupture²⁵. Published literature reports a natural annual mortality of 26.7% among patients with penetrating aortic ulcers²⁶. The European Association for Cardio-Thoracic Surgery (EACTS) and the European Society for Vascular Surgery (ESVS) acknowledge that stroke remains a major complication during aortic arch endovascular repair, with reported rates up to 14%²⁷⁻²⁹.

Measures to Reduce and Eliminate Bias

- 1) The clinical trial will be conducted in accordance with the trial protocol, national medical device clinical trial regulations and GCP principles as well as the company's standard operating procedures (SOP).
- 2) This clinical trial is a single-arm objective performance criterion study conducted simultaneously at multiple clinical centers across China. Subjects will be enrolled in accordance with the inclusion and exclusion criteria specified in the protocol. The enrolled study population shall maintain consistency with those investigated in previous studies, to minimize selection bias caused by incomparable baseline populations to the greatest extent possible.
- 3) Patients will be enrolled sequentially at each participating center and registered accordingly. A rigorous follow-up mechanism will be established, with sufficient communication maintained with the subjects to ensure high-quality follow-up, and to minimize missing data and participant dropout to the greatest extent possible.
- 4) The sponsor will provide training regarding the study protocol and the operation of the trial device to the investigators of this study to ensure that the investigators are fully aware of the study procedures and instructions regarding the proper use of the trial device.
- 5) The company will appoint qualified clinical trial investigators (CRAs) to visit and monitor the research center on a regular basis in order to maintain quality control and monitoring records, and to promptly communicate with the investigators regarding any problems found during the monitoring process.
- 6) They will furthermore be required to maintain and organize data and when data-related issues are found. Data analysts will check and confirm the data using a data challenge form to avoid

potential recording errors.

8.1.3. Trial Medical Device

Device Name: WeFlow-Tribranch embedded aortic Triple-branch arch Stent Graft system

Manufacturer: Hangzhou Endonom Medtech Co., Ltd.

8.1.4. Subject Selection

8.1.4.1. Selection Criteria (All of the following conditions must be met prior to enrollment)

1. Patients aged 18 to 80 years old
2. Patients diagnosed with aortic arch lesions requiring intervention, including true aortic arch aneurysms, pseudo-aortic arch aneurysms, and ulcers involving the aortic arch.
3. Patients showing a suitable vascular condition, including:
 - Ascending aorta length greater than 50 mm (from the aortic sinusoid junction to the proximal cardiac margin of the innominate artery).
 - Ascending aorta diameter ≥ 24 mm and ≤ 48 mm;
 - Proximal anchoring zone length ≥ 30 mm;
 - Innominate artery diameter ≤ 24 mm and ≥ 6 mm, length ≥ 20 mm;
 - Suitable arterial access for endovascular interventional treatment ;
4. Patients able to understand the purpose of the trial, participate in the trial voluntarily with informed consent form signed by the subject him/herself or his or her legal representative, and willing to complete follow-up visits as required under the protocol.

5. [REDACTED]

[REDACTED]

[REDACTED]

[REDACTED]

[REDACTED]

[REDACTED]

8.1.4.2. Exclusion Criteria (Enrollment will not be allowed if any of the following criteria are met)

1. Patients that have experienced systemic infection during past three months;

2. Neck surgery was performed within three months;
3. Previous endovascular interventional treatment involving the aortic arch was performed;
4. Infectious aortic disease、Takayasu arteritis, Marfan syndrome (or other connective tissue diseases);
5. Patients with severe stenosis, calcification, thrombosis or tortuosity;
6. Heart transplant patients;
7. Patients that have suffered MI or stroke during past three months;
8. Patients with Class IV heart function (NYHA classification);
9. Active peptic ulcers or upper gastrointestinal bleeding occurring within the previous three months;
10. Hematological abnormality, defined as follows: Leukopenia ($WBC < 3 \times 10^9/L$), acute anemia ($Hb < 90 \text{ g/L}$); thrombocytopenia ($PLT \text{ count} < 50 \times 10^9/L$), history of bleeding or coagulopathy;
11. Patients with renal insufficiency, serum creatinine $> 150 \mu\text{mol/L}$, and/or end-stage renal disease requiring renal dialysis;
12. Patients that are pregnant or breastfeeding;
13. Patients with allergies to contrast agents;
14. Patients with a life expectancy of less than 12 months;
15. Patients currently participating in other drug or device research;
16. Any other disease or abnormality that the investigators believe may hinder endovascular interventional treatment.

8.1.4.3. Dropout Criteria

All subjects who completed an informed consent form and were screened for entry into the clinical trial and who later withdrew, regardless of when and for what reason (excluding those who met the primary endpoint), will be counted as dropouts.

- 1) Subjects who withdraw themselves from the experiment for various reasons;
- 2) The ethics committee considers discontinuation of the study necessary for ethical and moral reasons due to one or more adverse events, especially serious adverse events;

- 3) The investigators consider it medically necessary for the subject to withdraw for the study;
- 4) There is a serious deviation from the trial protocol;
- 5) Subjects who are lost to follow up due to changes in work or living conditions or an accident, but for patients who are lost to follow up due to accidents such as traffic accidents, death, fractures, etc., a follow-up should be conducted promptly to determine whether or not there exists causal relationship with the trial device;
- 6) Subjects who are required to stop the trial for other reasons.

Notes: When a subject drops out due to a subject-related reason, the investigators should use all available avenues to contact the subject in order to inquire after the reason; if the subject drops out due to an adverse event, and the follow-up ultimately determines that there is a causal relationship with the trial device, the event must be recorded in the eCRF and the sponsor should be notified accordingly. All original data and source documents, i.e., retention files, which are also required for an intention-to-treat analysis (ITT Analysis), should be retained for all subjects who are enrolled and have entered the trial, regardless of whether they drop out.

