Follow-Up Period	After surgery, each subject will require 60 months of follow-up.
Patient Inclusion/ Exclusion Criteria	Inclusion Criteria 
 1. Patients aged 18 to 80 years old 2. Patients diagnosed with aortic arch lesions requiring intervention, including true aortic arch aneurysms, pseudo-aortic arch aneurysms, and ulcers involving the aortic arch. 3. Patients showing a suitable vascular condition, including: 
 • Ascending aorta length greater than 50 mm (from the aortic sinusoid junction to the proximal cardiac margin of the innominate artery). • Ascending aorta diameter ≥ 24 mm and ≤ 48 mm; • Proximal anchoring zone length ≥ 30 mm; • Innominate artery diameter ≤ 24 mm and ≥ 6 mm, length ≥ 20 mm ; • Suitable arterial access for endovascular interventional treatment ; 4. Patients able to understand the purpose of the trial, participate in the trial voluntarily with informed consent form signed by the subject

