8.1.5. Primary Endpoints

Rate of all-cause mortality and major stroke within 12 months after surgery. All-cause mortality includes cardiac death, non-cardiac death, and death of unknown cause. Major stroke

is defined as a modified Rankin Scale (mRS) score ≥ 2 at 90 days after stroke onset (see Appendix 2).

Calculation formula: (Number of cases with all-cause mortality or major stroke at 12 months postoperatively / Total number of treated subjects) $\times 100\%$

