9.4.2. Statistical Methodology and Analysis

1) General Principles

For quantitative variables, mean, standard deviation, median, minimum, maximum, lower quartile (Q1), and upper quartile (Q3) will be calculated. For categorical variables, the number and percentage of subjects in each category will be presented.

Comparison of general characteristics between the two groups will be analyzed using appropriate methods according to the type of variables. Between-group comparisons of quantitative data will be performed using the independent samples t-test (for homogeneous variance and normal distribution) or the Wilcoxon rank-sum test, depending on the data distribution. Categorical data will be analyzed using the chi-square test or Fisher's exact test (if the chi-square test is not applicable). Ordinal data will be analyzed using the Wilcoxon rank-sum test or the CMH test.

2) Completion Status and Demographic Analysis

The number of enrollments and completions for each center will be summarized and a list of fallout cases as well as a detailed list of reasons for non-completion will be created. Patients' demographic characteristics (age, sex, etc.), relevant medical history treatment, etc. will be described. A demographic analysis will be performed based on an FAS analysis set.

3) Primary Endpoints

Primary Endpoint: The incidence of all-cause death or major stroke within 12 months after the procedure. All-cause death includes cardiac death, non-cardiac death, and death of unknown cause. Major stroke is defined as a modified Rankin Scale (mRS) score ≥ 2 assessed at 90 days after stroke onset. The hypothesis testing is specified as follows:

Null Hypothesis: $H_0: P_T - P_C \leq \Delta$

Alternative Hypothesis: $H_1: P_T - P_C > \Delta$

$\alpha = 0.025$ (single tail)

At the significance level of $\alpha = 0.025$ (one-sided) and statistical power of $1 - \beta = 0.8$, the incidence rate of all-cause mortality or major stroke within 12 months post-procedure shall be statistically described, and its two-sided 95% confidence interval (95% CI) shall be estimated. The upper limit of the 95% CI

shall be compared with the Objective Performance Criteria (OPC). Statistical conclusions will then be drawn accordingly. If the upper limit of the 95% CI is lower than the objective performance criterion P_0 , the primary endpoint shall meet the trial requirements, and the investigational device can be considered to satisfy the requirements for clinical application.

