14.4. Reporting Procedures

14.4.1. Adverse Events

Adverse event data will be collected throughout the study, and the investigators will record and monitor all adverse events in the appropriate eCRF until recovery or stabilization occurs.

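### Section 8.1.4.3 lets implanted subjects become dropouts without requiring their 12-month vital and stroke status, and its wording on adverse events and death conflicts with the all-cause endpoint

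*Protocol*

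**What the plan says.** Section 8.1.4.3 (Dropout Criteria) counts as a dropout any consented and screened subject who later withdraws, at any time and for any reason, except those who have already met the primary endpoint. Item 3 covers the case where "The investigators consider it medically necessary for the subject to withdraw for the study", item 4 the case where "There is a serious deviation from the trial protocol", and item 6 any other reason. Nothing separates withdrawal before implantation from withdrawal after it.

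For a dropout the section requires three things:
- contact to learn the reason, if the reason is subject-related;
- for losses through accidents, among which item 5 names death, a prompt follow-up to decide whether the device was the cause;
- retention of the data already held, for the ITT analysis.

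Its note adds that the event must go into the eCRF when a subject "drops out due to an adverse event, and the follow-up ultimately determines that there is a causal relationship with the trial device".

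Elsewhere, section 8.1.5 defines the primary endpoint as "Rate of all-cause mortality and major stroke within 12 months after surgery", over the "Total number of treated subjects". Under section 14.4.1, "the investigators will record and monitor all adverse events in the appropriate eCRF until recovery or stabilization occurs". Section 14.1 defines an adverse event whatever its relation to the device. The notes to section 8.2.1 call for all adverse events from Visit 2 and for an mRS score 90 days after any stroke. The protocol summary says: "After surgery, each subject will require 60 months of follow-up".

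**The concern.** The graft is implanted in one procedure and stays in place. After that day no study treatment is left to stop, so withdrawal can only mean that observation ends. The endpoint needs to know, for each treated subject, whether death or a major stroke occurred by 12 months. The dropout section lets observation end for reasons other than the subject's refusal, and none of its three requirements supplies the missing outcome. Retaining data keeps what was collected before withdrawal and nothing after it. A later analysis plan cannot repair this, because it can only handle data that were collected.

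The section also looks at dropouts through device causality, whereas the endpoint ignores causality. A site that follows it literally could file a death judged unrelated to the device as a loss to follow-up. Section 9.5 would then treat that death as missing data of the unrelated kind.

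**Working it through.** **1. The plan's own figure.** Section 8.1.4.8 gives 72 valid cases and 20% dropout: 72 / (1 − 0.20) = 90, as stated. The allowance is 90 − 72 = 18 subjects. It covers every reason for dropout, so 18 is a ceiling for this point.

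**2. What can be lost.**

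| Situation | Rule | Result |
|---|---|---|
| Death or established major stroke before withdrawal | 8.1.4.3 excepts subjects who met the endpoint | Counts |
| Stroke before withdrawal, 90-day mRS due after it | 8.2.1 asks for the mRS; 8.1.4.3 does not say it continues | May be lost |
| Death or stroke after withdrawal | No ascertainment required | May be lost |
| Death judged unrelated to the device | 8.1.5 counts it; 8.1.4.3 item 5 and 9.5 allow it to be a loss or missing value | Contradictory |

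**3. What section 9.5 does with missing outcomes.** Those related or possibly related to the device or to dissection are imputed as failures. The others, including those arising from unrelated death, get best-case, worst-case and tipping-point analyses, and none of these is named as primary.

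**4. How many events decide the result.** Section 9.4.2 requires the upper limit of the two-sided 95% CI to lie below P0. P0 is blacked out and the interval method is not named. I assume P0 from 0.15 to 0.35 and the exact (Clopper-Pearson) limit, which for x events in n is the 0.975 quantile of Beta(x + 1, n − x). At P0 = 0.25, 14 of 90 gives 0.247 and passes, and 15 of 90 gives 0.260 and fails.

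| P0 (assumed) | 0.15 | 0.20 | 0.25 | 0.30 | 0.35 |
|---|---|---|---|---|---|
| Most events of 90 that pass | 6 | 10 | 14 | 18 | 22 |

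Up to P0 = 0.30, 18 unknown outcomes equal or exceed the whole passing count.

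**5. A smaller case.** Assume that 3 to 6 implanted subjects are withdrawn for reasons other than refusal, and that 20% to 40% of them have an unseen event. That is 3 × 0.20 = 0.6 to 6 × 0.40 = 2.4 events, or 0.7 to 2.7 percentage points of 90.

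**6. Effect on the one-sided type I error.** Let the true rate over all 90 equal P0. With k withdrawn subjects failing at rate f, the remaining subjects fail at c = (90·P0 − k·f) / (90 − k). For k = 6, f = 0.40 and P0 = 0.25, c = (22.5 − 2.4) / 84 = 0.239. The error is the probability that a Binomial(90 − k, c) count does not exceed the passing limit. That limit is the 90-subject limit for best case, the same limit minus k for worst case, and the limit for n = 90 − k for observed subjects only.

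| Scenario, over P0 = 0.15 to 0.35 | Type I error |
|---|---|
| All 90 observed | 0.013 to 0.022 |
| k = 3, f = 0.40, best case | 0.029 to 0.041 |
| k = 6, f = 0.40, best case | 0.061 to 0.072 |
| k = 6, f = 0.40, observed only | 0.061 at P0 = 0.15, 0.037 at 0.20, 0.022 to 0.023 from 0.25 up |
| k = 6, f = 0.40, worst case | at most 0.0013 |
| k = 18, f = 1.5 × P0, best case | 0.15 to 0.55 |
| k = 18, f = 1.5 × P0, observed only | 0.032 to 0.075 |
| k = 18, worst case | about 0 |

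The same lost outcomes make the test too lenient or too strict according to the imputation used.

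**The case against.** The strongest reply is that the protocol already protects most of this ground. The note says that a device-caused event must be recorded; it does not say that others need not be. Besides sections 8.2.1, 14.1 and 14.4.1, section 8.4 (item 6) has monitors confirm that all adverse events are recorded, and section 21.4 (item 8) has investigators document all of them. A reader might infer that recording is limited to device-caused events. The documents do not support that: they show a note out of line with the general rule.

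A reader might also infer that the observed rate must be biased downward because the withdrawn are the likely failures. That is not shown either. Events before withdrawal count, related missing data are imputed as failures, and the worst-case analysis errs the other way. A higher event rate in the withdrawn is plausible when the reason is medical, but no figure in the documents establishes it.

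Finally, requiring full visits after withdrawal would collide with withdrawal on ethics-committee grounds (section 8.1.4.3 item 2, section 15.2) and would impose scheduled CTA. That is a fair limit on the remedy.

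What stands is that no text requires 12-month vital and stroke status after withdrawal, that imputation cannot recover an outcome nobody sought, and that item 5 and the note do not fit an all-cause endpoint.

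**Conclusion.** The point holds as a gap in outcome ascertainment together with a conflict between passages, and it should be corrected. At most 18 of 90 outcomes are exposed under the plan's own allowance. Some of those will be refusals or true loss of contact, which no wording can fully recover. On the smaller assumption, 0.6 to 2.4 events are at stake, against passing counts of 6 to 22. Whether this matters for the decision depends on the imputation: with six subjects failing at 40%, the one-sided error is about 0.06 to 0.07 under best case and close to zero under worst case. P0, the exact interval, the number withdrawn and their event rates are all assumptions. Neither a fixed size nor a fixed direction of bias can be claimed.

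**What to change.** Amend section 8.1.4.3 in three places.

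1. For any implanted subject who stops scheduled visits for a reason other than refusing further contact or use of data, still collect vital status and stroke status to 12 months, with the 90-day mRS after any stroke, by telephone or from records. Ask subjects who withdraw consent to permit this. The consent form was not available, so check whether it already does. Leave ethics-committee and medical decisions on visits and procedures as they are.
2. Reword the note so that every adverse event leading to dropout is entered in the eCRF regardless of causality, in line with section 14.4.1.
3. State that any death within 12 months is a primary endpoint event and never a dropout or a missing value, and bring item 5 and the missing-data text in section 9.5 into line.

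The cost is a protocol amendment, possibly a consent wording change, and a few calls or record checks. No extra procedure is needed.
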